This study is designed to assess the efficacy and economics of two NPWT branded devices of wound healing outcomes. It is also designed to assess the effectiveness of negative pressure and negative pressure with continuous irrigation on multiple parameters of wound healing. It is a single-center, open-label, active controlled, parallel-group trial that aims to determine the efficacy of Quantum with simultaneous irrigation in the treatment of diabetic foot ulcers. Specifically, eligible participants will be randomized to receive either PRO negative press therapy with simultaneous irrigation; or PRO negative pressure therapy without irrigation; or KCI Ultra negative pressure therapy. Primary outcomes will include rates of wound healing, time to closure by secondary intention, and recurrence rate.

Study Objectives and Endpoints

Objective 1

- A) To compare clinical outcomes in Wounds treated with Negative Pressure Wound therapy with and without Simultaneous Irrigation.**

H1: The wound healing outcomes of patients treated with NPWT Pro will be non-inferior to the wound healing outcomes of patients treated with NPWT-KCI Ultra

Primary Endpoint:

- Comparison of reduction in wound volume between wounds treated with NPWT PRO and NPWT-KCI Ultra

Secondary Endpoints:

- Comparison of rate of wound healing in wounds treated with NPWT PRO and NPWT-KCI Ultra.

- Comparison of the following variables between the groups: granulation tissue integrity including hypergranulation state, time to close, flap/graft take, dehiscence, and reoccurrence.

B) To compare clinical outcomes in Wounds treated with NPWT PRO with and without Simultaneous Irrigation.

H1: Patients treated with NPWT with irrigation will have higher proportions of wounds that heal and faster wound healing trajectories compare to patients treated with NPWT without irrigation.

H2: Patients treated with Negative Pressure Wound therapy with Irrigation will have fewer wound complications such as infections, amputations, and foot-related hospital admissions.

Primary Endpoints:

- Primary Endpoint: Comparison of reduction in wound volume between wounds treated with NPWT PRO and NPWT PRO with simultaneous irrigation

Secondary Endpoints:

- Comparison of rate of wound healing in wounds treated with NPWT and NPWT with simultaneous irrigation

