If evaluation of the clinical indicators suggest the presence of significant bacterial infection of the wound, swab culture, utilizing swab technique [126] will be performed to confirm or reject the presence of significant bacterial infection severe enough to warrant the subject terminated from the study. The swab culture will be performed using a laboratory-provided swab that is pressed down over a 1 cm² area of the wound that is then delivered to the lab for analysis to determine Colony-Forming Units (CFUs) per gram of viable wound tissue and beta-hemolytic Streptococcus per gram of tissue. The findings of a positive or negative swab culture utilizing Levine's technique will be interpreted according to the following criteria:

- Positive culture indicating presence of bacterial infection: $\geq 1,000,000$ Colony-Forming Units (CFUs) per gram of viable wound tissue OR containing beta-hemolytic Streptococcus per gram of tissue at any level.
- Negative culture indicating absence of bacterial infection: $< 1,000,000$ Colony-Forming Units (CFUs) per gram of viable wound tissue OR no beta-hemolytic Streptococcus per gram of tissue at any level.

Tissue specimens will be obtained from the chronic wounds using 1) wound exudate, 2) broad Z-technique, and 3) Levine technique [126]. Acquisition of swab specimens was followed with a wound tissue biopsy. The diagnostic validity of each technique was determined by associating the quantitative culture findings of each swab specimen with the culture findings of concurrent tissue specimen (gold standard). Levine's technique performed best of the three swab techniques in terms of all four validity parameters: sensitivity was, specificity, positive predictive value, and accuracy.

Bio-burden

Bio-burden will be assessed using qPCR to quantify bacterial load from serial tissue specimens. Specific organisms that will be quantified using qPCR are listed in the table below. Bone, soft tissue will be sent to Research and Testing Laboratory (Lubbock, TX) for analysis.

Specific organisms (and two resistance factors) to be quantified using qPCR.			
E. faecalis	E. faecium	S. epidermidis	M. morgani
K. pneumonia	S. aureus	C. striatum	S. haemolyticus
S. agalactiae	S. marcescens	F. magna	S. mutans
S. pyogenes	H. influenzae	P. mirabilis	Vancomycin res.
C. albicans	M. catarrhalis	C. parapsilosis	Methicillin res.
P. aeruginosa	S. pneumoniae	A. baumannii	Total Bioburden

Osteomyelitis

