The inpatient stay and post-operative visits are covered under a 90-day global payment which is inclusive of all procedures, devices, testing and ancillaries associated with the surgical procedure, including NPWT. Subjects’ insurance will not be charged any additional amount for the NPWT devices used in the study. The KCI devices are standard at Parkland; Cardinal is providing their devices. But again, in neither situation would a subject or their third party pay or be charged anything additional.

Survival Analyses Models

The primary analytical method presented in this report is based on a time-to-event strategy using Kaplan-Meier estimates, followed by a log-rank test. This statistical procedure provides a comparison of the distribution of events between the 2 treatment groups. In addition to the event rates calculated for the post-baseline time points, the median time to 100% closure, 75% closure, and 76-100% wound bed granulation will also be calculated. This same methodology will also be used to compare the overall duration of treatment, and within the individual patient subsets defined by their outcome status.

A Cox proportional hazard model will be used to relate time to specific events to various risk factors. The main modeling strategies will look at the time to adverse events with time being measured from the time of surgery or the time of NPWT application until either an adverse event occurs, the patient is considered healed, or the end of the study. Cox proportional hazard model allows the independent variables to be continuous covariates or categorical or binary factors. The type of NPWT treatment will be the main independent variable. We will use multivariate proportional hazard regression analysis methods to investigate what factors are significant for non-healing patients or patients that have complications. Similar to the logistic regression, maximum likelihood estimates of model parameters along with tail probabilities (p-values) and confidence intervals for parameters

will be derived based on asymptotic inferences. For the proportional hazard model the ratio of the hazards for two subjects one with and one without diabetes, given that the subjects have the same values for other parameters can be estimated from the model coefficients. Repeated measures ANOVA and ANOVA will be used to evaluate changes in quantitative cultures and laser Doppler measurements over time and between treatment groups.

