For all serious adverse events, the investigator is obligated to pursue and provide information to Cardinal Health in accordance with the timeframes for reporting specified above. In addition, an investigator may be requested by Cardinal Health to obtain specific additional follow-up information in an expedited fashion. This information may be more detailed than that captured on the adverse event case report form. In general, this will include a description of the adverse event in sufficient detail to allow for a complete medical assessment of the case and independent determination of possible causality. Information on other possible causes of the event, such as concomitant medications and illnesses must be provided. In the case of a subject death, a summary of available autopsy findings must be submitted as soon as possible to Cardinal Health or its designated representative.

Non-Serious Adverse Event Reporting Requirements

All adverse events will be reported on the adverse event page(s) of the CRF. It should be noted that the form for collection of serious adverse event information is not the same as the adverse event CRF. Where the same data are collected, the forms must be completed in a consistent manner. For example, the same adverse event term should be used on both forms. Adverse events should be reported using concise medical terminology on the CRFs as well as on the form for collection of serious adverse event information.

Reporting Requirements to Regulatory Authorities

Adverse events reporting, including suspected serious unexpected adverse reactions, will be carried out in accordance with applicable local regulations.

Potential Risks of Study Participation

Participation in this clinical investigation presents low risks to subjects. Some risks are generalized and are listed in Tables below.

Potential Risks Associated with the Investigational Product

All risks known or anticipated based on prior experience, risk analysis or reasonable grounds are listed in the Instructions for Use. This protocol document will be updated in the presence of new information of relevance to the safety of the subject or the conduct of the study.

Risks	Disorders/Conditions

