5. Ensure that all associates, colleagues and employees assisting in the conduct of the study are informed about their obligations in meeting the above commitments.

6. Maintain adequate and accurate records in accordance with §21 CFR 312.62 and to make those records available for inspection by the Cardinal Health contact.
7. Ensure that an IRB that complies with the requirements of §21 CFR part 56 will be responsible for initial and continuing review and approval of the clinical study.
8. Promptly report to the IRB and the Cardinal Health contact all changes in the research activity and all unanticipated problems involving risks to subjects or others (to include amendments and IND safety reports).
9. Seek IRB approval before any changes are made in the research study, except when necessary to eliminate hazards to the patients/subjects.
10. Comply with all other requirements regarding the obligations of clinical investigators and all other pertinent requirements listed in § 21 CFR part 312.

12 Month Extension

After the end of the defined study period, the patients will be followed observationally by their electronic medical records for 12 months as it would not be feasible to ask them to return for an in-person evaluation as: patients have moved, no longer have correct contact information, as well as it would create a financial hardship on the patients to return for further visits. In order to more appropriately determine long term results from participation, a longer period of time of follow up is necessary. Related outcomes that we would like to follow over a 12-month duration are incidence of new foot ulcerations, re-ulceration of a previously healed foot wound, healing and time to healing of patients who took longer than the current study allows, duration of antibiotics received for foot infections, re-admissions to the hospital, need for subsequent surgery, amputation, loss of limb, and death. This expanded follow up period would provide valuable information to the long-term outcomes and complications of this high risk population and will help direct how future efforts may be better focused to reduce complications and improve outcomes.

Sending Samples and Data for Analysis

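### Kaplan-Meier closure rates have no rule for death or amputation of the wound site; under default censoring they overstate the proportion closed

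*Combined protocol and SAP*

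**What the plan says.** Under Survival Analyses Models: "The primary analytical method presented in this report is based on a time-to-event strategy using Kaplan-Meier estimates, followed by a log-rank test". Besides event rates at post-baseline times, "the median time to 100% closure, 75% closure, and 76-100% wound bed granulation will also be calculated". Study Groups and Design gives closure a prominent place: "Primary outcomes will include rates of wound healing, time to closure by secondary intention, and recurrence rate". Under Objective 1, however, the primary endpoints are reductions in wound volume, and time to closure is secondary.

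The documents foresee three ways of leaving the risk set without closure:

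- **Amputation.** Objective 1B, H2 predicts that irrigated patients "will have fewer wound complications such as infections, amputations, and foot-related hospital admissions". The 12 Month Extension also follows "need for subsequent surgery, amputation, loss of limb, and death".
- **Death.** Serious Adverse Event Reporting Requirements: "In the case of a subject death, a summary of available autopsy findings must be submitted as soon as possible".
- **Termination for infection.** Under Swab Culture, a culture is taken to confirm or reject "significant bacterial infection severe enough to warrant the subject terminated from the study".

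No section says how such a subject enters the time-to-closure analysis. There is no censoring rule for closure, no competing-risk method, and no rule that counts these subjects as not closed. The only rule on when time stops belongs to the Cox model for time to adverse events. There, time also ends at healing, so the same question arises in reverse.

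**The concern.** Kaplan-Meier assumes that a subject censored at a given week has the same later chance of closing as those still under observation. That cannot hold after death or amputation of the wound site. One minus Kaplan-Meier then estimates closure in a hypothetical setting where nobody dies or loses the wound site. Read as the proportion closed by week 12, it is too high, and the median time to closure is too short.

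At stake are the reported closure rates and medians. The sponsor says one purpose of the trial is to obtain data to power a larger multicenter study, so overstated closure rates would be carried forward. If the events differ much between arms, the comparison of closure is affected as well.

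**Working it through.** **Inputs from the documents.** Follow-up is up to 12 weeks. There are 90 subjects randomized 1:1:1, so 30 per arm. The sample size assumes closure of 60% without irrigation and 85–90% with it.

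**The plan's own figure.** The printed formula with 60% versus 90%, mean 0.75 and 80% power gives:

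- two-sided alpha 0.10: (1.645 × √0.375 + 0.842 × √0.33)² / 0.3² = 24.7, against a stated 25;
- two-sided alpha 0.05: the same with 1.960 gives 31.5, against a stated 31.

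These are comparisons of proportions, so the point below leaves the sample size unchanged.

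**Assumptions.** The documents give no 12-week rate for death or amputation. I take 5%, 10% and 15%, with constant hazards λ (closure) and μ (competing event).

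**Step 1: what a Kaplan-Meier figure corresponds to.** λ = −ln(1 − KM)/12 per week. μ is solved so that μ/(λ+μ) × (1 − e^(−12(λ+μ))) equals the assumed competing rate. The proportion closed is then λ/(λ+μ) × (1 − e^(−12(λ+μ))).

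| Kaplan-Meier closure | λ | 5% competing | 10% | 15% |
|---|---|---|---|---|
| 60% | 0.0764 | 58.0% | 56.0% | 54.0% |
| 90% | 0.1919 | 86.2% | 82.4% | 78.6% |

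Example for 60% and 10%: μ = 0.0136, so 0.0764/0.0900 × (1 − e^(−1.080)) = 0.560.

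The median moves too. For the 60% row, Kaplan-Meier gives ln 2/0.0764 = 9.1 weeks. The time at which the cumulative incidence reaches 50% is 9.4, 9.9 and 10.4 weeks.

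**Step 2: effect on the gap between arms.** Kaplan-Meier shows 90 − 60 = 30 points. The corresponding true gaps are:

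- 5% competing in both arms: 86.2 − 58.0 = 28.2, so Kaplan-Meier exaggerates the benefit;
- 10% without irrigation, 5% with: 86.2 − 56.0 = 30.2, almost no change;
- 15% without, 5% with: 86.2 − 54.0 = 32.2, so Kaplan-Meier understates it.

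**Step 3: effect on the test.** Simulation with 30 per arm, two-sided 0.05 and constant hazards. Competing-event subjects are either censored or kept at risk to week 12 as not closed.

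| True closure | Competing events | Log-rank, censored | Kept as not closed |
|---|---|---|---|
| 60% vs 60% | 5% vs 5% | about 5% | about 5% |
| 60% vs 60% | 10% vs 5% | 5–6% | 5–6% |
| 60% vs 60% | 20% vs 5% | 10–11% | about 5% |
| 60% vs 85% | 5% vs 5% | 75–76% | about 70% |
| 60% vs 85% | 10% vs 5% | about 69% | 68–69% |
| 60% vs 85% | 20% vs 5% | 48–49% | 62–64% |

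In the third row, equal true closure of 60% appears as 70.1% versus 62.1%. In the arm with 20%, the total hazard over 12 weeks is −ln(1 − 0.6 − 0.2) = 1.609 and the closure share is 0.6/0.8, so 1 − e^(−1.207) = 0.701. In the other arm, −ln(0.35) × 0.6/0.65 = 0.969, so 1 − e^(−0.969) = 0.621.

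**The case against.** The plan never says that these subjects will be censored; it is silent. That stands, and the defect is a missing rule. But the named estimator has a default, and the default is the one that overstates closure.

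The log-rank test is a legitimate test of the cause-specific closure hazard, and Gray's test answers a different question. That stands too, so replacing one with the other is a trade-off, and at 5% versus 5% the ordinary log-rank has more power. The objection does not rescue the event rates and medians, which will be read as probabilities and times of closure.

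Three stronger readings are tempting, and the documents do not support them:

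- **That the bias shrinks a true irrigation benefit.** H2 predicts fewer amputations and infections with irrigation, but says nothing of death or study termination and gives no rates. At a given competing rate the overstatement is larger in the arm with more closure, so the gap can be exaggerated, unchanged or reduced (Step 2).
- **That it makes the two devices look alike in the non-inferiority comparison.** The primary endpoint for PRO versus KCI is wound volume, with a separate non-inferiority procedure. H2 predicts no difference in failures between those arms, and any bias could go either way.
- **That termination for infection also rules out closure.** Such a wound may close after the subject leaves. This is informative censoring, probably in the same direction because these wounds are less likely to close.

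Finally, the distortion of the test needs a strong imbalance, and nothing in the documents shows that 20% versus 5% is likely.

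**Conclusion.** The point holds as a gap in the closure analysis. Kaplan-Meier event rates and medians are planned for an outcome that death and wound-site amputation preclude, and no rule covers those subjects. Under default censoring the 12-week proportion closed is overstated by about 2 to 6 points at 60% and 4 to 11 points at 90%, for 5% to 15% competing events. These sizes rest on assumed rates and constant hazards.

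The direction of the effect on the arm comparison is not fixed. It is negligible at 10% versus 5%. At 20% versus 5% the log-rank rejects about 10% of the time when closure is equal at 60%, and power for 60% versus 85% falls from about 62–64% to 48–49%.

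The correction should be made, but it does not undermine the design: the endpoints named as primary under Objective 1 are volume reductions, and the sample size is unaffected.

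**What to change.** Add to Survival Analyses Models, before data are analysed by arm:

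1. Estimate closure by week and median time to closure by cumulative incidence (Aalen-Johansen), with death and amputation of the wound site as competing events. Keeping these subjects in the risk set as not closed to week 12 gives the same estimate if nobody is otherwise lost earlier.
2. Treat termination for infection as informative censoring. Use closure status from the medical record where available; the 12 Month Extension already relies on electronic records and lists healing. Add a sensitivity analysis that counts these subjects as not closed.
3. Keep the log-rank, described as a test of the cause-specific closure hazard, and report Gray's test beside it.
4. Report deaths, wound-site amputations and infection terminations by arm.

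The cost is SAP wording, a standard software routine and some record review, with no change to sample size or treatment. The downside is that reported closure rates become slightly less favourable.

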- Presents with an existing chronic or traumatic wound, sub-acute or dehisced wound, partial-thickness burn, ulcer (such as a diabetic or pressure ulcer), flap or graft as diagnosed by a qualified and certified medical practitioner (M.D., D.O., or D.P.M)
- Wound presents with full thickness loss of epidermis and dermis
- The presentation of a wound that in the opinion of the investigators will require surgical debridement, and the wound is expected to be a good candidate for NPWT.
- $ABI \geq 0.5$ or toe pressures >30 PVR/mmHg
- Subject is willing and able to abstain from partaking in any other form of treatment for his or her wound during the active treatment phase of this study , other than the study procedures described herein.
- 18 years of age or older

Exclusion Criteria

Subjects that satisfy any one or more of the following exclusive conditions criteria outlined below will be excluded from participation in the clinical study.

- Does not present with an existing chronic or traumatic wound, sub-acute or dehisced wound, partial-thickness burn, ulcer (such as a diabetic or pressure ulcer), flap or graft, or a definitive diagnosis cannot be made, as diagnosed by a qualified and certified medical practitioner (M.D., D.O., or D.P.M)
- Wound does not present with full thickness loss of epidermis and dermis

- ABI<0.5 or toe pressures <30 PVR/mmHg
 - Subject is not willing or is not able or it is not medically prudent for the subject to abstain from partaking in any other form of treatment for his or her wound during the active treatment phase of this study, other than the study procedures described.
 - Subject is unwilling or unable to use the NPWT device at home
 - Active Charcot arthropathy
 - Collagen vascular disease
 - Scleroderma
 - Non-enteric and unexplored fistula
 - Necrotic tissue with eschar present after debridement
 - General skin disorder in the area of the wound such as psoriasis or penicilitis
 - Malnutrition (Defined as BMI < 19)
 - Hypercoagulable state based on documentation in their medical record
 - Acute deep vein thrombosis
 - Current active malignancy in the wound
 - Current melanoma or history of melanoma at the wound
 - Current active or history of invasive squamous cell carcinomas at the wound
 - Sepsis (defined as positive blood culture with leukocytosis) and temperature >101.5 at the time of screening
 - Significant hematologic disorders EXCLUDING anemia
-
- HIV
 - Fever at screening > 101.5
 - Deep X-ray therapy

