The wound will be measured using the eKare InSight. The eKare Insight photo/measurement system is a wound imaging device that quickly, precisely and consistently measures the area, depth and volume of wounds and tracks their healing progress. This technique has been shown to be highly reproducible [120, 121]. The Insight measurement system functions in a similar fashion as an Aranz Unit and within our own group we have published studies on the equivalency of these two devices to accurately measure wound size [122].

Granulation Tissue Estimation

Granulation tissue will be estimated at each study visit and recorded as a percentage of wound bed coverage and change in volume measurements.

Human Wound Healing PCR Array

The Human Wound Healing RT² Profiler™ PCR Array profiles the expression of 84 key genes central to the wound healing response. Wound healing progresses via three overlapping phases: inflammation, granulation and tissue remodeling. After cutaneous injury, a blood clot forms, and inflammatory cells infiltrate the wound, secreting cytokines and growth factors to promote the inflammation phase. During the granulation phase, fibroblasts and other cells differentiate into myofibroblasts, which deposit extracellular matrix (ECM) proteins. Simultaneously, angiogenesis occurs, and keratinocytes proliferate and migrate to close the wound. In the final tissue remodeling phase, apoptosis eliminates myofibroblasts and extraneous blood vessels, and the ECM is remodeled to resemble the original tissue. Dysregulation of this last tissue remodeling phase leads to fibrosis. This array contains genes important for each of the three phases of wound healing, including ECM remodeling factors, inflammatory cytokines and chemokines, as well as growth factors and major signaling molecules. Using real-time PCR, you can easily and reliably analyze the expression of a focused panel of genes involved in wound healing, tissue injury and repair with this array. The tissue will be sent to Research and Testing Laboratory in Lubbock, Texas or UTSW core services for evaluation of the following:

Extracellular Matrix and Cell Adhesion

- ECM Components: COL14A1, COL1A1, COL1A2, COL3A1, COL4A1, COL4A3, COL5A1, COL5A2, COL5A3, VTN.
- Remodeling Enzymes: CTSG, CTSK, CTS2L2, F13A1, F3 (Tissue Factor), FGA (Fibrinogen), MMP1, MMP2, MMP7, MMP9, PLAT (tPA), PLAU (uPA), PLAUR (uPAR), PLG, SERPINE1 (PAI-1), TIMP1.

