Osteomyelitis will be diagnosed when radiographic and clinical signs are consistent with bone infection. This diagnosis will be confirmed with imaging, bone biopsy, culture or histopathology as most applicable to the individual subject. The bacterial pathogens and sensitivities from bone and soft tissue cultures will be recorded and direct antibiotic therapy applied, if necessary [79].

Study Procedures

Procedures and Evaluations During the Research

The time period from Day 0 to up to 12 weeks will encompass the study therapy administration and evaluation phase. The precise therapy employed will be determined according to subject randomized group allocation, and the duration of the study therapy administration phase will be determined according to individual subject wound healing and status progression and safety evaluations. The study therapy administration phase will comprise the

following progressive activities, as applicable, and will be initiated in the inpatient clinic setting: therapy administration, , and weekly or standard of care wound healing and safety evaluation. The study therapies are delivered in continuous mode throughout the individual subject's entire study therapy administration phase; with the only consistent interruption being for the three times a week wound dressing changes. There will likely be other minimal daily interruptions such as to allow for subject showering and bathing. Therapy administration phase will continue until study wound is ready for closure by secondary intention, after which time the therapy will be discontinued.

Therapy Administration

- Therapy phase to be continued until wound is ready for closure by secondary intention
 - During this therapy administration phase, all subjects will receive NPWT therapy for 4 weeks or until the wound is deemed ready for surgical closure, whichever occurs first. This time point will serve as the individual subject's study evaluation endpoint.
 - Study wound readiness for surgical closure in this study is defined as the time point (evaluation visit) at which the following three factors pertaining to the status of the study wound are determined to co-exist by the study investigator:
 - deep structures (bone, tendon, joint) are covered with granulation tissue
 - the wound depth is < 2 mm
 - the wound bed is ready for skin graft, delayed primary closure or rotational flap to cover the defect.

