Wound Assessment/ Debridement	X	X	X		X		
Tissue /bone ¹ / wound culture samples for qPCR cultures & bioburden analysis		X	X (Subsequent surgery)				

			while Inpatient)				
NPWT/NWPT (i) randomization/dressing application/changes		X	X	X (Weeks 2-4)	X (Weeks 2-4)		NWPT for maximum 4 weeks after baseline(Day0 surgery) if wound is not closed in the hospital
SF-36 Questionnaire	X					X	
Hyperspectral Imaging Analysis	X						To occur prior to surgery
Discharge Instructions			X		X		
Offloading			X	X	X		At hospital discharge & continuing to Week 12
Adverse Events		X	X	X	X	X	
Current/concomitant antibiotics	X	X	X	X	X	X	
Wound imaging/measurement		X	X		X	X	While active study wound is present
Neuropathy Disability Score in Patients with Diabetes	X						

¹ Only if performed as a necessary part of standard of care.

² Subjects who heal before week 12 will exit the study and complete EOS visit.

Biostatistics

Sample Size Justification:

There are no published data with the Cardinal PRO negative pressure wound therapy (NPWT) device with or without irrigation in order to determine an estimate of the sample size for this study. One of the purposes of this project is to obtain data, so we can power a larger multicenter study. Even though the KCI NPWT device with irrigation has been commercially available, there is little data about volume change or wound healing in the population we are studying.

The previous sample size justification was based on a comparison of the proportion of wounds expected to achieve surgical closure. The proportion of subjects with closed wound was 62% using traditional KCI NPWT and 94% using NPWT with periodic irrigations with Prontosan. For the sample size, we estimated 85-90% wound closure with NPWT with irrigation and 60% wound closure with NPWT without irrigation. We assume the NPWT devices (KCI and Cardinal) without irrigation would have similar results.

Equations

The following formula was used to estimate the required sample size, n , for the relative difference in proportions P_1 and P_2 .

$$n = \frac{\left(Z_{\alpha/2} \sqrt{2P(1-P)} + Z_{\beta} \sqrt{P_1(1-P_1) + P_2(1-P_2)} \right)^2}{(P_1 - P_2)^2}$$

where

$$P = \frac{P_1 + P_2}{2}$$

Using the formula above and assuming 90% wound closure with NPWT with irrigation and 60% wound closure with NPWT without irrigation and a type I error of 0.1, the required sample size is about 25. If a Type I error of 0.05 is assumed, then the required sample size is about 31.

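### The primary log-rank test leaves Day 0 wound size unused, so power that one prespecified covariate could recover is forgone

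*Combined protocol and SAP*

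**What the plan says.** All references are to the combined protocol and SAP.

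- **Primary method.** Biostatistics, Survival Analyses Models, makes the primary method a "time-to-event strategy using Kaplan-Meier estimates, followed by a log-rank test". No covariate or stratification factor is given. The section adds that "the median time to 100% closure, 75% closure, and 76-100% wound bed granulation will also be calculated".
- **Cox models.** The same section plans Cox regression with type of NPWT as the main independent variable, but "The main modeling strategies will look at the time to adverse events". A multivariable Cox model is to look for factors linked to non-healing or complications. Neither model lists wound size, and neither is called the primary treatment comparison.
- **Randomisation.** Allocation is 1:1:1 by sealed envelope, opened at the end of the initial debridement. No stratification factor is stated.
- **Wound size.** Under Digital Photos & Wound Measurement, the imaging device "measures the area, depth and volume of wounds and tracks their healing progress". The Schedule of Events marks wound imaging at Baseline Day 0.
- **Eligibility.** Many wound types are admitted. The requirement on extent is "Wound presents with full thickness loss of epidermis and dermis"; no minimum or maximum area, depth or volume is set.
- **Readiness for surgical closure.** Therapy Administration lists three conditions that must hold together. One is that "the wound depth is < 2 mm".
- **Sizing.** The Biostatistics section sizes the trial on closure, "assuming 90% wound closure with NPWT with irrigation and 60% wound closure with NPWT without irrigation", and gives 85-90% as the range expected with irrigation. Enrolment is 90, so 30 per arm.

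**The concern.** A wide mix of wounds with no size limit makes a large spread in Day 0 volume likely. Other things equal, a larger or deeper wound should take longer to close. When a baseline variable predicts the outcome, a comparison that ignores it has less power than one that uses it. The variable is already being collected, so the gain needs no new data.

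The stake is greatest where the trial is weakest. At the lower end of the plan's own range (85% closure with irrigation), 30 per arm leaves the unadjusted comparison well under 80% power. The planned Cox models do not fill the gap, because they address adverse events or search for risk factors.

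**Working it through.** **1. The plan's sample size.** Inputs from Sample Size Justification and Equations: P1 = 0.60, P2 = 0.90, mean P = 0.75, power 80%.

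n = [z(α/2)·√(2P(1−P)) + z(β)·√(P1(1−P1) + P2(1−P2))]² / (P1−P2)²

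- α = 0.10: (1.645×0.6124 + 0.842×0.5745)² / 0.09 = 24.7. The plan says about 25.
- α = 0.05: (1.960×0.6124 + 0.842×0.5745)² / 0.09 = 31.5. The plan says about 31.

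The plan's figures reproduce, apart from rounding. With 30 per arm and α = 0.05, the same two-proportion comparison has 78% power for 90% closure and 59% for 85%.

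**2. The same rates as a log-rank test.** Assume exponential times and complete follow-up to week 12.

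- 60% versus 90%: HR = ln(0.10)/ln(0.40) = 2.51. Events = 30×0.60 + 30×0.90 = 45. Power = Φ(√(45/4)·ln 2.51 − 1.96) = 87%.
- 60% versus 85%: HR = ln(0.15)/ln(0.40) = 2.07. Events = 43.5. Power = 67%.

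**3. What adjustment adds at the planned closure rates.** Simulation: 30 per arm, exponential times, censoring at end of follow-up, two-sided 5%, 3,000 trials per row. One standardised baseline covariate (log size) acts on the closure hazard. Its strength is assumed and is shown as the hazard ratio per SD, in whichever direction favours closure. Both arms' overall closure rates are held at the stated values.

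| HR per SD (assumed) | 60% vs 90%: log-rank | Adjusted Cox | Gain, points | 60% vs 85%: log-rank | Adjusted Cox | Gain, points |
|---|---|---|---|---|---|---|
| 1.00 | 87.5% | 86.6% | −0.9 | 67.0% | 65.6% | −1.4 |
| 1.35 | 88.6% | 90.7% | 2.1 | 68.5% | 70.3% | 1.8 |
| 1.65 | 89.9% | 94.2% | 4.3 | 70.9% | 77.8% | 6.9 |
| 2.12 | 91.7% | 98.5% | 6.8 | 72.0% | 87.7% | 15.7 |
| 2.72 | 91.7% | 99.7% | 8.0 | 71.7% | 94.5% | 22.8 |

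Repeat runs reaching about 3 per SD put the gains at about 2-3 points at the low end, and at 8-9 points (60% vs 90%) and 22-23 points (60% vs 85%) at the high end. The rounded ranges are therefore 2 to 9 and 2 to 23.

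**4. Validity.** With no treatment effect (4,000 trials each), rejection rates were 5.7% for log-rank and 5.6% for adjusted Cox when the covariate had no effect. At 2.72 per SD they were 5.0% and 4.9%. Both tests hold their level.

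**5. A different framing.** If the covariate-conditional HR is instead fixed at 2.51, log-rank power at 1.65 / 2.12 / 2.72 per SD is 78% / 66% / 57%, against 85% / 83% / 83% adjusted. The median unadjusted HR is 2.27 / 2.08 / 1.94. But true irrigation-arm closure then drops from 90% to 86.8% / 84.1% / 81.6%, so much of the fall in log-rank power comes from a smaller true difference.

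**6. Chance imbalance.** The between-arm difference in a standardised covariate has SD √(2/30) = 0.26. A difference above 0.3 SD has probability 2×[1 − Φ(0.3/0.258)], or about 1 in 4.

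**The case against.** The strongest reply is that the test is sound and the need for adjustment is unproven. Several stronger conclusions that a reader might draw are not supported:

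- **That wound size largely determines time to closure.** The documents do not quantify this. Depth is one of three readiness conditions judged by the investigator. That rule also defines readiness for surgical closure, whereas the events listed with the log-rank analysis are 100% closure, 75% closure and granulation. The 75% event may already be scaled to baseline size. Prognostic value is plausible, and no more.
- **That the log-rank test's power falls to between 57% and 78%.** This holds only if the conditional hazard ratio is fixed, which lowers irrigation-arm closure, at the two stronger settings to below the plan's 85-90%. At the planned 60% versus 90%, log-rank power is not reduced.
- **That the treatment effect is biased toward no effect.** A log-rank test gives no hazard ratio. An unadjusted Cox hazard ratio nearer 1 reflects non-collapsibility: it is a marginal quantity, not a biased one.
- **That chance imbalance invalidates the test.** Randomisation already allows for it in the type I error. Adjustment improves precision; it does not rescue validity.

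Two further replies carry weight. The named primary endpoint for the irrigation comparison is "Comparison of reduction in wound volume between wounds treated with NPWT PRO and NPWT PRO with simultaneous irrigation", so the status of time to closure needs settling first; that is a separate and larger matter. The plan also describes itself partly as a source of data for a larger trial, which softens a power argument. Neither removes the point: time to closure by secondary intention is also listed among the primary outcomes under Study Groups and Design, the sizing rests on closure, and the primary method is time-to-event.

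**Conclusion.** The point holds as an efficiency recommendation, not as a flaw in validity. The primary log-rank test ignores a baseline measurement that the schedule already provides, and neither the randomisation nor the Cox models make up for it. If log wound size carries a hazard ratio of about 1.35 to 3 per SD, adjustment is worth about 2 to 9 points of power at 60% versus 90% closure and about 2 to 23 points at 60% versus 85%. If size is not prognostic, it costs about 1 point.

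These figures rest on an assumed prognostic strength, exponential times, proportional hazards, a correctly specified log-linear size effect and no dropout (no rate is stated). Times were treated as continuous, although visits are weekly or per standard of care. The gain is material mainly if the closure difference is nearer the lower end of the plan's range.

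**What to change.** In Survival Analyses Models, for the time-to-closure comparison of PRO with and without irrigation:

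- Make the primary test the treatment effect from a Cox model containing treatment and log Day 0 imaged volume as the single prespecified covariate.
- State that this volume is measured after the initial debridement and before the first study dressing. Day 0 is also the day of surgery, and the Schedule of Events does not say which side of the debridement the imaging falls.
- Name the closure event to which the test applies.
- State that the hazard ratio is conditional on baseline volume.
- Keep the Kaplan-Meier curves and the unadjusted log-rank test as supporting analyses.

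The cost is a change to the analysis text and a clear imaging time; no new measurement or patients are needed. The small downsides are a conditional rather than marginal hazard ratio and reliance on the Cox model's form. The supporting log-rank test shows whether the conclusion depends on that form.
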